In our recently completed Phase I fixed dose iCO trial, we also found an excellent correlation between measured and predicted COHb levels using the CFK equation¹¹². While the CFK equation is a well-validated model of CO uptake that accurately predicts the rise in COHb following CO exposure in humans with normal lung function⁹⁷⁻¹⁰³, it had not been previously used in ARDS patients with impaired gas exchange before. We found an excellent correlation in participants treated with 100 ppm iCO (Spearman $r= 0.8614$; $p<0.0001$), but an even stronger correlation in subjects treated with 200 ppm iCO (Spearman $r=0.916$; $p<0.0001$) (Figure 8A). Modeling the 200 ppm Cohort 2 data with linear regression revealed a slope of 1.112 (95% confidence interval [CI] [1.003, 1.22]), a y-intercept of -0.6632 (95% CI [-1.174, -0.1522]), and goodness-of-fit $R^2=0.9204$ ($p<0.0001$). Bland-Altman plots also demonstrated excellent agreement between measured and CFK equation-predicted COHb levels (Figure 8B) with a mean difference between measured and predicted COHb levels of 0.1467 ± 0.2738 in Cohort 2 (200 ppm).

The above predictions using the CFK equation were made using a MATLAB-generated computer program to estimate DLCO using the baseline and 20 minute COHb. The estimated DLCO was then input into the programmed CFK equation and used to predict the 60, 75, and 90 minute COHb levels. This program was validated by generating the previous published curves (Figure 1) that were derived from predicted values using the CFK equation¹⁰¹.

[figure not shown]

Figure 8. CFK equation accurately predicts COHb levels in ARDS patients.

CFK Equation For Precision-Based iCO Dosing

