3 OBJECTIVES AND ENDPOINTS

| OBJECTIVES | ENDPOINTS | JUSTIFICATION FOR ENDPOINTS |
|--|--|--|
| Primary | | |
| To evaluate the safety and accuracy of a CFK equation-based personalized iCO dosing algorithm in patients with pneumonia and/or sepsis-induced ARDS. | 
1. Safety of iCO, defined by the incidence of pre-specified administration-related AEs and SAEs.
 
Administration-related SAEs are: 1) myocardial infarction; 2) stroke; 3) new onset arrhythmia requiring DC cardioversion; 4) worsening hypoxemia^{1,2}; 5) COHb $\geq 10\%$; and 6) increase in lactate by ≥ 2 mmol/L.
 
2. Accuracy of the CFK equation-based personalized iCO dosing algorithm. This will be assessed by comparing the measured COHb level at 90 minutes and the target COHb level of 6-8%.
 | 
1. Safety of iCO: These administration-related SAEs were used in our prior Phase I fixed-dose iCO trial and are SAEs that could potentially occur if there were decreased delivery of oxygen. A COHb level $\geq 10\%$ was chosen as an administration-related SAE as the goal COHb is 6-8%.
 
2. Accuracy of personalized iCO dosing approach: The accuracy of the iCO dosing algorithm to achieve the target COHb level (6-8%) will be evaluated.
 |
| Secondary | | |
| To determine the effect of low dose iCO therapy on clinical outcomes in patients with | 1. Lung Injury Score (LIS) on days 1-5 and day 7 2. PaO ₂ /FiO ₂ on days 1-5 and day 7 | LIS, PaO ₂ /FiO ₂ , OI, and Vd/Vt have been shown to correlate with VFDs and |

| OBJECTIVES | ENDPOINTS | JUSTIFICATION FOR ENDPOINTS |
|--|---|---|
| pneumonia and/or sepsis-induced ARDS. | 3. Oxygenation index (OI) on days 1-5 and day 7 4. Dead space fraction (Vd/Vt) on days 1-3 and day 7 5. Sequential Organ Failure Assessment (SOFA) scores on days 1-5, 7, 14, and 28 6. Ventilator-free days (VFDs) to day 28 7. ICU-free days to day 28 8. Hospital-free days to day 60 9. Hospital mortality to days 28 and 60 10. Neurocognitive function at 3 and 6 months | mortality in prior ARDS studies. |
| Exploratory | | |
| To examine the effects of low dose iCO therapy on biologic readouts in patients with pneumonia and/or sepsis-induced ARDS. | Blood and urine biomarkers of mitochondrial dysfunction (mtDNA), inflammasome activation (IL-18) and necroptosis (RIPK3). Lipid mediators (LM) and specialized pro-resolving mediators (SPMs). | Our preliminary data suggest that CO may modulate these biomarkers. |

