9.2 SAMPLE SIZE DETERMINATION

As the primary endpoint of this Phase Ib trial is safety, this sample size of 36 (2:1 CO:placebo) was chosen based on a probability to estimate the mean difference between measured and predicted COHb levels in the CO group within 0.5% with 95% confidence to support the accuracy of the CFK equation.

Our preliminary data from our Phase Ia trial demonstrate that the CFK equation is highly accurate at predicting COHb levels following a 20 minute exposure to 200 ppm iCO ($r=0.916$, $R^2=0.9204$; $p<0.0001$). The mean difference between measured and predicted COHb levels was 0.1467 ± 0.2738 . Using a more conservative estimate of standard deviation (SD)=0.6, we will have >99% probability that 95% confidence intervals around the mean difference between measured and predicted COHb levels will be -0.353% to 0.647%. Our calculation includes an 8% dropout rate.

The goal of the safety evaluation for this study is to identify safety concerns associated with CO administration. The ability of the study to detect administration-related AEs or SAEs can be expressed by the true event rate above which at least one SAE would likely be observed and the true event rate below which no events would likely be observed. Specifically, for the CO arm of the study (n=24), there is a 90% probability of observing at least one AE if the true background rate of that AE is 10% and a 97% probability of observing at least one AE if the true background rate of that AE is 15%. For the placebo arm of the study (n=12), there is an 83% probability of observing at least one AE if the true background rate of that AE is 15% and a 91% probability of observing at least one AE if the true background rate of that AE is 20%. In our Phase Ia trial, there were no administration-related AEs and no SAEs related to study product or procedures.

Probabilities of observing one or more events between the groups are presented in **Table 6** below for a range of possible true AE rates. These calculations provide a more complete picture of the sensitivity of this study design to identify potential safety problems with CO.

Table 6. Probability of observing 1 or more events between the groups for different true AE rates

| CO group | | | Placebo Group | | |
|----------|--------------|-----------------------------|---------------|--------------|-----------------------------|
| n | True AE rate | Power to detect ≥ 1 AE | N | True AE rate | Power to detect ≥ 1 AE |

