9.4.2 ANALYSIS OF THE PRIMARY SAFETY ENDPOINT(S)

We hypothesize that iCO will be safe and well-tolerated and that our iCO dosing algorithm will be accurate

in achieving target COHb levels.

We will examine all AEs including pre-specified administration-related AEs by the type of event, as well as by body system class, and will report proportions and 95% CI. We will compare the occurrence of specific AEs in each arm by the χ^2 test, and the number of AEs per patient in each arm by the Wilcoxon-Mann-Whitney test.

COHb levels will be summarized descriptively reporting mean, standard deviation, median, minimum, and maximum at each time point, each day, by treatment arm. The mean difference between predicted and measured COHb levels with 95% confidence intervals will be presented for the iCO group. Repeated measures analysis of variance (ANOVA) will be used to assess the effects of treatment, time (over 3 days), and the interaction between time and treatment for 90-minute COHb levels. ANOVA will be repeated to assess the effects of treatment, time (over 3 days), entry criteria (ARDS/Sepsis vs. Non-ARDS/Sepsis Pneumonia vs. Non-ARDS/non-Sepsis Pneumonia), and two-way/three-way interactions of time, treatment and entry criteria. We will also compare the occurrence of COHb $\geq 10\%$ in each arm by the χ^2 test.

Accuracy of the CFK equation-based personalized iCO dosing algorithm to achieve target COHb levels will also be analyzed by Spearman correlation and Bland-Altman plots using measured vs. predicted COHb levels and modeled using linear or non-linear regression.

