9.4.5 SAFETY ANALYSES

The primary endpoint is safety of iCO, defined by the incidence of pre-specified administration-related AEs and SAEs. Administration-related SAEs are: 1) myocardial infarction; 2) stroke; 3) new onset arrhythmia requiring DC cardioversion; 4) worsening hypoxemia^{1,2}; 5) COHb \geq 10%; and 6) increase in lactate by \geq 2 mmol/L. The primary endpoint is also accuracy of the CFK equation-based personalized iCO dosing algorithm to achieve a COHb level of 6-8%.

We will examine all AEs including pre-specified administration-related AEs by the type of event, as well as by body system class, and will report proportions and 95% CI. We will compare the occurrence of specific AEs in each arm by the χ^2 test, and the number of AEs per patient in each arm by the Wilcoxon-Mann-Whitney test.

For AEs not included in the protocol defined grading system, the CTCAE Version 5.0 guidelines will be used to describe severity. The CTCAE term, start and stop date, severity, relationship, expectedness, and outcome will be reported for all AEs. A separate table will report the incidence of pre-specified administration-related AEs per arm.

COHb levels will be summarized descriptively reporting mean, standard deviation, median, minimum, and maximum at each time point, each day, by treatment arm. The mean difference between predicted and measured COHb levels with 95% confidence intervals will be presented for the iCO group. Repeated measures analysis of variance (ANOVA) will be used to assess the effects of treatment, time (over 3 days), and the interaction between time and treatment for 90-minute COHb levels. ANOVA will be repeated to assess the effects of treatment, time (over 3 days), entry criteria (ARDS/Sepsis vs. Non-ARDS/Sepsis Pneumonia vs. Non-ARDS/non-Sepsis Pneumonia), and two-way/three-way interactions of time, treatment and entry criteria. We will also compare the occurrence of COHb $\geq 10\%$ in each arm by the χ^2 test.

Accuracy of the CFK equation-based personalized iCO dosing algorithm to achieve target COHb levels will also be analyzed by Spearman correlation and Bland-Altman plots using measured vs. predicted COHb levels and modeled using linear or non-linear regression.

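### The second primary endpoint is attainment of COHb 6-8% at 90 minutes, but every planned accuracy analysis measures agreement with the CFK prediction instead

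*Combined protocol and SAP*

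**What the plan says.** The endpoint table in section 3 lists accuracy of the dosing algorithm as the second primary endpoint and says how it is judged: "This will be assessed by comparing the measured COHb level at 90 minutes and the target COHb level of 6-8" per cent. Section 9.1 lists it again in terms of achieving that range, and 9.4.5 confirms its status: "The primary endpoint is also accuracy of the CFK equation-based personalized iCO dosing algorithm to achieve a COHb level of 6-8" per cent.

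Sections 9.4.2 and 9.4.5 give the same set of COHb analyses:

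- Descriptive summaries: "COHb levels will be summarized descriptively reporting mean, standard deviation, median, minimum, and maximum at each time point, each day, by treatment arm".
- Agreement in level: "The mean difference between predicted and measured COHb levels with 95% confidence intervals will be presented for the iCO group".
- Repeated-measures ANOVA of 90-minute COHb on treatment and day, then repeated with entry criteria.
- A chi-square test for COHb of 10% or more, by arm.
- Accuracy methods, which "will also be analyzed by Spearman correlation and Bland-Altman plots using measured vs. predicted COHb levels and modeled using linear or non-linear regression".

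The sample size in 9.2 rests on a "probability to estimate the mean difference between measured and predicted COHb levels in the CO group within 0.5% with 95% confidence".

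Two design features bear on this. The algorithm computes a dose aimed at 7% at 90 minutes, held within 200-500 ppm (6.1.3, 6.1.5). A session is stopped if COHb exceeds 8% (6.1.7), and the 90-minute measurements are then taken at the time of stopping (8.5.3).

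**The concern.** The trial hypothesis is that the algorithm achieves 6-8%. The only place that says how this is judged is section 3, and its comparator is the target range. In section 9 the comparator becomes the CFK prediction. Neither 6-8% nor 7% is the reference value in any listed analysis, and the one COHb threshold that is analysed, 10%, is a safety limit.

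Agreement and attainment are different questions. A subject whose dose is held at a bound can be predicted accurately to miss the target, and will then count as good agreement. Where the bound does not bind, the mean difference and limits of agreement do bear on the target, but a precise mean difference says little about how many individuals fall within one percentage point of 7%.

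Section 9 also leaves *predicted* undefined, both as to what it is and at which time points. In Phase I the fitted equation was "used to predict the 60, 75, and 90 minute COHb levels". Nor does it say how a value recorded at an early stop, for a reason other than COHb above 8%, is to be set against the target.

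Followed as written, the plan could support a statement that dosing was accurate without ever reporting how many iCO subjects reached the target.

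**Working it through.** **Inputs.** Phase I bias 0.1467 and SD 0.2738 (2.2.9, 9.2); planning SD 0.6, precision 0.5% and 8% dropout (9.2); 24 iCO subjects (4.1), so 24 × 0.92 ≈ 22 after dropout; aim 7%, range 6-8% (6.1.3). SDs of 0.8 and 1.0 are assumptions, used to show sensitivity.

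**1. The plan's own figure reproduces.** The probability that a 95% t-interval has half-width at most 0.5 is P(χ² with n−1 df ≤ (n−1)·n·(0.5/(t·0.6))²). For n = 24, t = 2.069 and the bound is 23 × 24 × (0.5/1.241)² ≈ 89.6, which gives more than 0.9999. For n = 22 the probability is also above 0.9999. The stated interval is 0.1467 ± 0.5 = −0.353 to 0.647. The arithmetic in 9.2 is sound, but it concerns agreement with prediction.

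**2. What that precision implies for the target.** With dosing aimed at 7%, no binding bound and normal error with bias b = 0.1467 and SD s:

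share in 6-8% = Φ((1 − b)/s) − Φ((−1 − b)/s); half-width = t·s/√24.

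| SD | Source | In 6-8% | Below 6% | Above 8% | Half-width, n = 24 |
|---|---|---|---|---|---|
| 0.2738 | Phase I | 99.9% | 0.0% | 0.1% | 0.12 |
| 0.6 | Planning value | 89% | 2.8% | 7.7% | 0.25 |
| 0.8 | Assumed | 78% | 7.6% | 14.3% | 0.34 |
| 1.0 | Assumed | 68% | 12.6% | 19.7% | 0.42 |

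Every half-width is inside 0.5. The limit is reached at s = 0.5 × √24 / 2.069 = 1.18, where the share in range is 60%. So the planning criterion can be met while two subjects in five miss.

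**3. The descriptive summaries do not fix the share.** Both of these sets of 24 values have mean 7.1, SD 0.6 to one decimal, median 7.1, minimum 5.8 and maximum 8.4:

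- Set A: 5.8; 5.9 (×2); 7.0 (×8); 7.1 (×8); 7.3; 8.1 (×3); 8.4. Sum 170.4, SD √(9.38/23) = 0.64. In range: 8 + 8 + 1 = 17.
- Set B: 5.8; 6.5 (×5); 6.9 (×3); 7.1 (×10); 8.0 (×4); 8.4. Sum 170.4, SD √(8.54/23) = 0.61. In range: 5 + 3 + 10 + 4 = 22.

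An integer-programme search on a 0.1 grid, with mean and SD within 0.04 of the stated values, confirms 17 and 22 as the extremes. With SD 1.0 and range 5.0-9.0, the count can be anywhere from 8 to 22. Holding the SD to within 0.01 raises the lower ends only to 18 and 10. These are constructed extremes, not forecasts.

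**4. Phase I.** In the 200 ppm cohort the measured-minus-predicted difference was 0.1467 ± 0.2738, while mean COHb was 4.9% and the maximum 6.87% (2.2.5, 2.2.9). Dosing was fixed, so this says nothing about how the algorithm will perform. It shows only that good agreement can coexist with a mean below target.

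**5. Precision for the proportion.** Exact (Clopper-Pearson) 95% intervals: 18/24 gives 53-90%; 21/24 gives 68-97%; 18/22 gives 60-95%; 20/22 gives 71-99%.

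**The case against.** The best defence has five parts.

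- *Predicted equals target.* If *predicted* means the planned 90-minute value and the dose is not at a bound, measured minus predicted is measured minus 7, and the limits of agreement speak to the target. This stands in part. But section 9 does not adopt that definition, and a predictor fixed near 7% would make the Spearman correlation and the regression uninformative, so the methods named do not fit it. It also fails when a bound binds.
- *The descriptive summaries suffice.* 90-minute COHb is reported by day and arm, and a reader can hold it against 6-8%. True for the average and the extremes; the number who missed cannot be recovered.
- *A proportion is only one reading of section 3.* That section names no statistic, and an interval for the mean 90-minute level would also be a comparison with the target. This is fair, but no such comparison is planned, and a mean inside 6-8% does not show that individuals reached it, which is the purpose of personalised dosing.
- *The low shares need SDs well above Phase I.* Correct. At the two SDs the documents give, the shares are 99.9% and 89%. The larger SDs show what the 0.5% criterion would tolerate; they are not predictions.
- *A fuller SAP may exist.* Section 6.1.4 refers to a Statistical Analysis Plan for a calculation that section 9 does not contain. The finding is therefore limited to the document supplied.

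Early stops are also partly covered: a session stopped for COHb above 8% would normally supply an out-of-range value. Only stops for other reasons are left open.

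**Conclusion.** The concern holds and should be fixed. As supplied, the plan has no analysis that answers the second primary endpoint as section 3 defines it, and its planning precision addresses a different quantity. That precision is compatible with anything from nearly all subjects in range (99.9% at the Phase I SD) down to 60% (SD 1.18). These shares assume normal error around 7%, the Phase I bias and no binding of the dose bound; they ignore the stop above 8%. How often the bound will bind cannot be derived from the documents, so no figure is put on it. This is a mismatch between endpoint and analysis, not an arithmetic error. The data needed are already scheduled, so the risk is that the reading of a primary endpoint is settled after the COHb values have been seen.

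**What to change.** In 9.4.2 and 9.4.5:

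- Make the primary accuracy statistic the proportion of iCO subjects with 90-minute COHb in 6-8% on the first treatment day, with an exact 95% confidence interval and the counts below 6% and above 8%. Using the first day gives one value per subject.
- Count sessions stopped early for COHb above 8% as out of range. Show sessions stopped early for other reasons separately.
- Summarise all treatment days with a method that allows for repeated days within a subject.
- Keep the measured-versus-predicted analyses as supportive, and state what *predicted* is and at which time points it is compared.

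In 9.2, add the precision for the proportion, using the exact intervals above for 24 treated and 22 evaluable subjects.

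The cost is protocol and SAP wording only; no extra data are needed. The drawback is that the headline accuracy result will have a wider interval and may look less favourable than agreement with the prediction.

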6.1.3 DOSING AND ADMINISTRATION

Inhaled CO or placebo air will be administered to participants via the COventDS, which will be calibrated and connected to the ventilator (**Figure 9**). Ventilator management will follow the ARDS Network lower tidal volume (6 mL/kg PBW) protocol¹³. Subjects randomized to CO will be administered iCO at 200 ppm for 20 min as a “test dose” on each treatment day to determine in real-time each subject’s CFK equation-determined personalized dose.

COHb levels will be measured before and after the 20 min test dose, and these two levels entered into the CFK equation calculator program to estimate DL_{CO} and compute the iCO dose to achieve a COHb level of 7% (target 6-8%) at 90 min. After the iCO dose is determined, subjects will be administered iCO at the CFK equation-determined personalized dose (200-500 ppm) but **not to exceed 500 ppm or 90 min total (including test dose)**. Subjects randomized to placebo will be administered medical grade air.

The study drug will be administered for up to 90 minutes daily for three days following randomization or until discontinuation of mechanical ventilation, whichever occurs first. For patients who have a tracheostomy, the equivalent of extubation for the purposes of this protocol will be breathing via tracheostomy with unassisted breathing.

The study drug concentration will be monitored continuously with the COventDS built-in analyzer and blood will be drawn at serial time points for arterial blood gas (ABG) analysis and safety monitoring of COHb levels as described in **Section 6.1.4**.

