6.1.5 CO DOSING ALGORITHM USING THE CFK EQUATION

For subjects randomized to iCO, iCO (200 ppm) will be administered for up to 20 minutes as a "test dose" on each day to determine the subject's CFK equation-determined dose. The COHb level will be measured prior to the test dose and 20 minutes after the test dose. These two COHb levels will be used in the CFK equation to determine each subject's specified dose in order to achieve a COHb level of 6-8%. After the CO dose is determined, subjects will be administered inhaled CO at the algorithm-determined dose- not to exceed 500 ppm or 90 minutes total (including test dose). Subjects randomized to placebo will be administered medical grade air.

1. Arterial or venous blood will be drawn for baseline blood gas analysis and COHb measurements prior to iCO or placebo administration.
2. Subjects randomized to CO will be treated with inhaled CO at 200 ppm for 20 minutes (test dose).
3. After 20 minutes, blood will be drawn for COHb measurement.
4. DLCO will be estimated using the baseline and 20 min COHb in the CFK equation calculator program, and used to compute the iCO dose to achieve a COHb level of 7% (target 6-8%) at 90 minutes.
5. Dose will be adjusted (200-500 ppm) in subjects randomized to CO based on CFK equation-determined dose.
6. Blood will be drawn for COHb measurements at 20 min, 40 min, 60 min, 75 min, 90 min, and 3 hours. Blood will also be drawn for blood gas analysis at 90 min.

On days 1-3, a total of approximately 3 mL of blood will be drawn during the study drug administration for safety monitoring of COHb levels and blood gas analysis.

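### The dose is chosen so that predicted 90-minute COHb is 7%, so correlating or regressing measured on predicted COHb cannot show target accuracy, and no listed analysis gives the share of sessions within 6-8%

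*Combined protocol and SAP*

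**What the plan says.** Section 3 defines the accuracy endpoint by the 90-minute value: "This will be assessed by comparing the measured COHb level at 90 minutes and the target COHb level of 6-8"%. It names no statistic.

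Sections 6.1.3 and 6.1.5 describe the dosing. After a 20-minute test dose at 200 ppm, the calculator estimates DLCO from the baseline and 20-minute COHb and uses it to "compute the iCO dose to achieve a COHb level of 7% (target 6-8%) at 90 min". The result is bounded: "Dose will be adjusted (200-500 ppm) in subjects randomized to CO based on CFK equation-determined dose". Table 5 (Section 8.5.3) shows one dose adjustment per session, at 20 minutes. Treatment stops if COHb exceeds 8% (Section 6.1.7), and the 90-minute measurements are then taken at the stop time (Section 8.5.3).

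Section 9.4.2, repeated in 9.4.5, lists these COHb analyses:
- mean, SD, median, minimum and maximum by time point, day and arm;
- the mean predicted-measured difference with 95% CI in the iCO group;
- repeated-measures ANOVA of 90-minute COHb;
- a chi-square comparison of COHb of 10% or more.

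It adds that accuracy "will also be analyzed by Spearman correlation and Bland-Altman plots using measured vs. predicted COHb levels and modeled using linear or non-linear regression". The time points for this last analysis are not stated. Section 9.2 bases the sample size on the ability to "estimate the mean difference between measured and predicted COHb levels in the CO group within 0.5% with 95% confidence".

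**The concern.** Correlation and regression of measured on predicted values are informative when predictions differ between sessions. They did in the Phase I trial, where the dose was fixed at 100 or 200 ppm and patients with different uptake had different predicted COHb. There the estimated DLCO was "used to predict the 60, 75, and 90 minute COHb levels" (Section 2.2.9), and the reported Spearman r was 0.916 at 200 ppm. The present trial chooses each dose to remove that variation. The same statistic, carried over, no longer answers the endpoint's question of whether measured 90-minute COHb falls within 6-8%. The statistic that would answer it directly, the share of sessions in the window, is not listed. A correlation reported under the accuracy endpoint could be read as evidence for or against the algorithm when it is evidence of neither.

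**Working it through.** **Inputs.** Set-point 7%, window 6-8%, dose limits 200-500 ppm (Sections 6.1.3, 6.1.5). Phase I measured-minus-predicted difference: mean 0.1467, SD 0.2738; planning SD 0.6; precision target 0.5; 24 iCO subjects, about 22 after 8% dropout (Section 9.2). Table 4 for uptake over time.

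**1. The plan's own figure.** CI half-width = t × SD/√n. With SD 0.6 this is 2.069 × 0.6/√24 = 0.253, or 2.080 × 0.6/√22 = 0.266. The probability that the half-width is at most 0.5 exceeds 0.9999, so the stated >99% reproduces, and 0.1467 ± 0.5 gives -0.353 to 0.647. The sample-size basis is not in question.

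**2. Predicted COHb at 90 minutes.** If the computed dose lies within 200-500 ppm and is given to 90 minutes, predicted = 7 by construction. The SD of predicted is 0, so Spearman and the slope of measured on predicted are undefined. In a Bland-Altman plot against the mean, difference = M - 7 and mean - 7 = (M + 7)/2 - 7 = (M - 7)/2. The difference is then exactly twice (mean - 7), which is an artificial trend. The limits of agreement are unaffected.

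**3. When some sessions are capped (illustrative).** Model: 24 sessions, measured = predicted + normal error (mean 0, SD 0.2738), uncapped prediction 7, capped prediction set to one assumed value. Spearman is averaged over simulated trials; the in-window share comes from normal probabilities.

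| Capped sessions | Capped at 5.5%: Spearman / in 6-8% | Capped at 6.5%: Spearman / in 6-8% |
|---|---|---|
| 1 | 0.35 / 96% | 0.28 / 99.8% |
| 3 | 0.57 / 88% | 0.46 / 99.6% |
| 6 | 0.75 / 76% | 0.60 / 99% |
| 12 | 0.87 / 52% | 0.70 / 98% |

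In both columns the correlation rises with the number capped, whether attainment falls by almost half or hardly moves.

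**4. How often the cap might bind.** Table 4 by superposition: the extra response per ppm at 70 minutes, interpolated from the 500 and 200 ppm rows, is about 0.0131. The average ARDS patient then needs about 200 + (7 - 3.8)/0.0131 = 444 ppm and reaches about 3.8 + 300 × 0.0131 = 7.7% at 500 ppm. Across assumed uptake CVs of 15-50%, baselines of 0.75% or 1.97% and error SDs of 0.2738 or 0.6, the cap bound in about 3-48% of sessions, and the median 90-minute Spearman ran from 0.08 to 0.85. With 3-4% capped it was undefined in 25-29% of simulated trials.

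**5. Pooling earlier times.** In the same simulations, pooling 40-90 minutes gave median Spearman of about 0.92-0.99, while the median share of sessions in 6-8% ranged from 67% to 100%. Much of that correlation is COHb rising with time: from Table 4, the average patient's path is about 3.4, 5.0, 6.0 and 7.0% at 40, 60, 75 and 90 minutes. Predictions at 40-75 minutes also differ somewhat between patients through baseline and 20-minute COHb.

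**6. What the mean difference alone allows.** Setting t × SD/√n = 0.5 gives SD 1.13 (n=22) or 1.18 (n=24). There an unbiased algorithm with no dose limits places 62% or 60% of sessions in 6-8%. At the documents' SDs the figures are about 99.9% (0.2738) and 90% (0.6).

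**The case against.** The correlation and regression are supplementary, and the sample size rests on the mean difference and its CI. A reader might infer that the trial could report a mean difference near zero and hide that a third or more of sessions missed the target. The documents do not support that. It needs an error SD of 1.13-1.18, about four times the Phase I value and nearly twice the planning value. The planned SD, minimum and maximum would show it, and the limits of agreement would be about ±2.2 to ±2.3 points against a window of ±1.

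A reader might also infer that capping means missing the target. It need not: a capped session can be predicted anywhere below 7%, and 6-7% is in range, as the 6.5% column shows. Nor are predictions without any spread at every time point, since those at 40-75 minutes vary between patients. Section 9.4.2 fixes neither the direction of the regression nor the x-axis of the Bland-Altman plot. If predicted is regressed on measured, a constant prediction gives slope 0 rather than an undefined slope, though that is no more informative.

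Finally, Section 6.1.4 refers to a rule in a Statistical Analysis Plan that Section 9 does not contain, so a fuller plan may exist. The statement about the missing proportion is limited to the documents at hand.

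These points reduce the consequences. They do not restore meaning to a correlation with a constant, or supply the in-range proportion.

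**Conclusion.** The concern holds in a limited form. At 90 minutes, the endpoint's time point, the planned correlation or regression of measured on predicted COHb is undefined or mainly reflects dose limits. Pooled over earlier times it largely reflects elapsed time, with some between-patient spread. Neither form measures whether the algorithm reaches 6-8%. The endpoint is defined against that window, and no listed analysis reports the share within it.

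The 90-minute result follows from the dosing rule and needs no simulation. The capping and pooled figures rest on assumed uptake variation, capped values and error structure, and figures at SD 1.0 or above go beyond the SDs in the documents; all are illustrative. How often the cap will bind is unknown, and the conclusion does not depend on it. The mean difference with CI, the SD, minimum and maximum, and the limits of agreement stand, as do the dosing rule and the sample size. The change should be made, but its absence does not invalidate the trial.

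**What to change.** In Sections 9.4.2 and 9.4.5:

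- **Add the target statistic.** Report the proportion of iCO sessions with end-of-treatment COHb of 6-8%, overall and by day, with a CI that allows for repeated sessions per subject. Count sessions stopped for COHb above 8%, and capped sessions below 6%, as misses. List sessions stopped early for other reasons separately.
- **Keep the mean difference and limits of agreement** as the agreement measures. Define predicted as the CFK value at the delivered dose and actual time. Plot the difference against delivered dose or estimated DLCO, not against the mean.
- **Do not use the correlation or regression as evidence of target accuracy.** If kept for comparison with Phase I, state the time points and label it as a description of CFK fit.
- **List dose-limited sessions.** Comparing the 20-minute DLCO estimate with one back-calculated from later COHb values is optional.

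The cost is a text change before database lock. COHb at each time point (Table 5) and delivered dose (Section 6.2.1) are already recorded, and dosing and sample size do not change. The main downside is imprecision: 22 of 24, with one session per subject, has an exact 95% CI of 73-99%.
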